#### 8.3.1. Time Period and Frequency for Collecting AE and SAE Information

All SAEs will be collected from the signing of the ICF until 30 days after the last day of study participation.

All AEs will be collected from the signing of the ICF until the EOS/ET time point specified in the SoA (Section [1.3](#)).

All SAEs will be recorded and reported to the Sponsor or designee immediately and under no circumstance should this exceed 24 hours, as indicated in Section [10.3](#). The Investigator will submit any updated SAE data to the Sponsor within 24 hours of it being available.

Investigators are not obligated to actively seek AE or SAE after conclusion of the study participation. However, if the Investigator learns of any SAE, including a death, at any time after a participant has been discharged from the study, and he/she considers the event to be reasonably related to the study intervention or study participation, the Investigator must promptly notify the Sponsor.

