- y For an individual participant, if the echocardiogram cannot be performed without sedation (e.g., due to age), the echocardiogram should not be performed. The omission of an echocardiogram due to sedation requirement should not be considered a protocol deviation. In the event of rescreening, if a participant had been screened for this study within the last 3 months and had echocardiogram data sent to the central over-readers, repeat of the echocardiogram will not be required during the rescreen.

z Participants or parent(s)/legal guardian to be queried as to the ongoing burden of the study (Section 2.3.2).

aa For participants aged birth to 12 months, 13 to 24 months, 2 to 5 years, 5 to 7 years, and 8 to 11 years, the Peds QL will be completed by parental proxy, and the PedsQL family module will be completed for all participants (Section 8.1.4).

bb To include medical resource utilization questions and the WPAI:PH V2.0 CPV, both to be completed by the parent/guardian (Section 8.10).

cc Adverse events to be collected from the time of ICF signature through the End of Study/Early Termination Visit. Serious adverse events to be collected from the time of ICF signature through 30 days after the after last day of study participation.

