Study DCR-PHXC-104 was a multicenter, Phase 1, randomized, placebo-controlled, double-blind, single-dose trial of nedosiran in patients with PH3. The primary objective was to evaluate the safety profile of nedosiran in patients with PH3. The secondary objectives were to characterize the plasma PK of nedosiran and to determine the effect of nedosiran in lowering Uox after single-dose administration in patients with PH3. Six participants were randomized: 4 to nedosiran and 2 to placebo; all 6 randomized participants received one dose of study drug and completed the study.

Overall, nedosiran was well tolerated. All TEAEs were mild in severity. No TEAEs were considered serious or treatment related and no participant was withdrawn from the study due to a TEAE. There were no treatment-related trends in vital sign, physical examination, or ECG data observed between the nedosiran and placebo groups.

The efficacy endpoint was not met, as no participants achieved a > 30% decrease from baseline in 24-hour Uox on 2 consecutive visits. However, at Day 85, all participants in the nedosiran group experienced decreases in 24-hour Uox from Baseline, with a mean decrease of 24.5%. Two participants in the nedosiran had greater than 30% decreases in 24-hour Uox at a single visit. Similar trends were not observed in the 2 placebo-arm participants. As such, further evaluation of the efficacy of nedosiran in participants with PH3 is warranted.

Studies DCR-PHXC-301 (long-term roll-over study in patients with PH1, PH2, or PH3) and DCR-PHXC-204 (a 6-month open-label study in patients with severe renal impairment or ESRD) are ongoing. Both studies include participants < 18 years of age.

Nedosiran has an acceptable safety profile in both healthy volunteers and participants with PH1, PH2, and PH3. No significant safety findings have emerged from completed or ongoing studies.

Please see the Nedosiran IB for additional details of these clinical studies.

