### **2.3.5. Overall Benefit:Risk Conclusion**

At present, no therapies are approved by regulatory authorities for the treatment of patients with PH2 or PH3. Lumasiran, a treatment for PH1, is approved in a limited number of countries, including the European Union. A number of supportive therapies are also used in an attempt to mitigate some of the effects of the disease, but affected patients are at considerable risk of serious complications like renal stones, nephrocalcinosis, renal failure, and systemic tissue damage due to oxalate deposition. Combined liver-and-kidney transplantation is the only causative therapy but is associated with short- and long-term complications as well.

Thus far nedosiran treatment has shown potential benefit to reduce or prevent the excess oxalate production in the liver. If sustained, this could eliminate the need for a liver transplantation.

The potential risks with nedosiran include low elevations of liver function tests, muscle damage, and stimulation of pattern recognition receptors (e.g., Toll-like receptors) leading to cytokine release, inflammation, and ISRs. These risks can be monitored and should be reversible after drug discontinuation. The results from the completed study, DCR-PHXC-101, demonstrate the potential for nedosiran to bring patients into a near-normal or normal range of their 24-hour Uox values. Continuous risk-benefit assessments will be conducted by the Sponsor, the Medical Monitor of the CRO, and the SRC on an ongoing basis.

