**Prior/Concomitant Therapy**

6. Use of an RNAi drug within the last 6 months
7. History of 1 or more of the following reactions to an oligonucleotide-based therapy:
  - a. Severe thrombocytopenia (platelet count  $\leq 100,000/\mu\text{L}$ )
  - b. Hepatotoxicity, defined as ALT or AST > 3 times the upper ULN and total bilirubin >  $2 \times \text{ULN}$  or INR > 1.5
  - c. Severe flu-like symptoms leading to discontinuation of therapy
  - d. Localized skin reaction from the injection (graded severe) leading to discontinuation of therapy
  - e. Coagulopathy/clinically significant prolongation of clotting time

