### **8.3.5. Pregnancy**

Details will be collected of all pregnancies in female participants occurring after the start of study intervention and until 12 weeks after the last dose of study intervention.

If a pregnancy is reported, the Investigator should inform the Sponsor within 24 hours of learning of the pregnancy and should follow the procedures outlined in Section 10.5.

Abnormal pregnancy outcomes (e.g., spontaneous abortion, fetal death, stillbirth, congenital anomalies, and ectopic pregnancy) are considered SAEs.

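### AE and SAE collection ends by exit date, not last dose, so new events are sought only briefly in children who leave early or finish without entering Study 301

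*Protocol*

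**What the plan says.** Protocol 8.3.1 sets both collection periods. For AEs: "All AEs will be collected from the signing of the ICF until the EOS/ET time point specified in the SoA". For SAEs: "All SAEs will be collected from the signing of the ICF until 30 days after the last day of study participation". Footnote cc of the Schedule of Activities gives the same AE rule: "Adverse events to be collected from the time of ICF signature through the End of Study/Early Termination Visit". Section 8.3.1 adds: "Investigators are not obligated to actively seek AE or SAE after conclusion of the study participation". After that point the duty is to report an SAE that the investigator happens to learn of and considers reasonably related.

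SAP 4.1.1.6 ends the treatment-emergent period at the study completion date on the end-of-study form. The SAE summaries in SAP 4.3.1.2.1 are of treatment-emergent SAEs.

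Two other rules decide who is affected. Protocol 7.1.1 says that stopping study intervention is not leaving the study and that the remaining scheduled visits should be done. Under 7.2, a child who leaves the study has an early discontinuation visit if possible, with no interval from the last dose set.

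Elsewhere the protocol does use a period tied to the last dose. Section 8.3.5 collects pregnancies "occurring after the start of study intervention and until 12 weeks after the last dose of study intervention", and the contraception rules in 5.1 and 10.5.2 use the same 12 weeks.

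**The concern.** The drug is given monthly, and the protocol treats 12 weeks after the last dose as a period that still matters for pregnancy. Its account of Study DCR-PHXC-104, a single-dose study, reports that "at Day 85, all participants in the nedosiran group experienced decreases in 24-hour Uox from Baseline", which suggests that activity can outlast a dosing interval. Section 2.3.5 says of the known risks: "These risks can be monitored and should be reversible after drug discontinuation".

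A window that closes at the exit visit gives the least off-drug observation to two groups: children who leave soon after a dose, and completers who are not dosed and observed further in Study 301. Some of the first group may leave for safety reasons. Section 8.3.2 notes that in neonates, infants and toddlers non-specific symptoms may be the only sign of a reaction, so unprompted reporting after exit is a weak substitute for asking. What is at stake is incomplete ascertainment of events that begin after exit, in a small study where each such event counts.

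**Working it through.** The documents state no length of follow-up after the last dose, so there is no figure of theirs to reproduce. The lengths follow from the schedule.

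**Inputs.** Last scheduled dose Day 150 (±5) and EOS Day 180 (±5), from Protocol 1.3, Table 1. AE end: EOS/ET visit. SAE end: last day of participation + 30 days. Comparison interval: 12 weeks × 7 = 84 days, from Protocol 8.3.5. Day 85 in Study 104, assuming the single dose was on Day 1: 85 − 1 = 84 days.

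**Child stays to Day 180, last dose on day L.** AE days = 180 − L. SAE days = 210 − L. Shortfall = 84 minus the result, where positive.

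| Last dose | AE days | SAE days | AE short of 84 | SAE short of 84 |
|---|---|---|---|---|
| Day 1 | 179 | 209 | 0 | 0 |
| Day 30 | 150 | 180 | 0 | 0 |
| Day 60 | 120 | 150 | 0 | 0 |
| Day 90 | 90 | 120 | 0 | 0 |
| Day 120 | 60 | 90 | 24 | 0 |
| Day 150 | 30 | 60 | 54 | 24 |

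With the visit windows, the Day 150 row runs for AEs from 175 − 155 = 20 to 185 − 145 = 40 days, and for SAEs from 50 to 70 days.

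**Child leaves, with the ET visit g days after the last dose.** AE days = g. SAE days = g + 30, taking the ET visit as the last day of participation. The value of g is an assumption, because the protocol sets none.

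| g | AE days | SAE days | AE short of 84 | SAE short of 84 |
|---|---|---|---|---|
| 0 | 0 | 30 | 84 | 54 |
| 14 | 14 | 44 | 70 | 40 |
| 30 | 30 | 60 | 54 | 24 |

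AE cover reaches 84 days only if g is at least 84; SAE cover only if g is at least 54.

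**End date at 12 weeks.** 150 + 84 = Day 234, which is 54 days after Day 180 and 24 days after Day 210.

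**Scheduled contacts.** Table 1 has no column after EOS/ET. The one later item is a pregnancy test 2 to 3 weeks after the last dose in a participant of childbearing potential who leaves prematurely (footnote v; 10.5.3). Nothing else is scheduled to support the 12-week pregnancy window.

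**Number affected.** The synopsis plans about 25 enrolled and 20 completing, a difference of 5. Protocol 4.1 and 9.2 and SAP Section 5 say about 25 screened, so those 5 could include children never dosed. The number of completers not entering Study 301 is not given. No count can be derived.

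**The case against.** A reader might infer that harms go unsought in every child who stops the drug. Section 7.1.1 rules that out. A child last dosed by Day 90 who stays has at least 90 days of AE collection, longer than a completer's.

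A reader might also infer that reversibility is not observed. For identified events it is: 8.3.3 follows SAEs and non-serious AEs of special interest to resolution or stabilization, 8.3 keeps investigators responsible for AEs that are serious, related or led to stopping the drug, 8.2.6 repeats clinically significant abnormal laboratory tests, and Appendix 6 (10.6) follows possible liver injury to normal or baseline. The ET visit itself includes laboratory tests, ECG, examination and an antibody sample. Only events that begin after exit are missed.

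Nor does the Day 85 result show late toxicity. It is a mean 24.5% fall in urinary oxalate in 4 treated PH3 participants, in a study whose efficacy endpoint was not met. The contraception interval and the exclusion for "Use of an RNAi drug within the last 6 months" are not presented as safety-observation periods. Section 8.4 asks for overdose monitoring until the drug is no longer detected, at least 28 days, and the completers' windows compare reasonably with that.

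All of this stands, and it narrows the point and lowers its priority. It does not remove it: following known events does not find new ones, and the duty after exit is passive and limited to SAEs considered related.

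**Conclusion.** The point holds in a limited form and is minor. Collection of AEs, SAEs and treatment-emergent events ends by visit or participation date, whatever the date of the last dose. The consequence is confined to new-onset events in two groups:

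- children who leave the study early, with 0 to 30 days (AE) and 30 to 60 days (SAE) after a dose when the ET visit falls within 30 days of it;
- children who do not enter Study 301 and were last dosed at Day 150 (AE about 30 days, range 20 to 40; SAE about 60, range 50 to 70) or at Day 120 (AE about 60 days).

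The first group may include children under 6 who meet the liver criteria with no alternative cause. Appendix 6 says they are discontinued from the study, which is not reconciled with 7.1.1.

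The 84-day yardstick is the protocol's own pregnancy and contraception interval, borrowed here as a reasonable length. It is not a demonstrated period of risk. No AE or SAE timing rule in the documents is broken.

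**What to change.** For participants who do not enter Study 301, collect AEs and SAEs until the later of the current end point or 12 weeks after the last dose. Add one telephone contact at that time, of the Day 15 and Day 45 type, covering AEs, SAEs and, where relevant, pregnancy. For children who were withdrawn, make the call if the parent agrees.

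Amend Protocol 8.3.1, footnote cc and SAP 4.1.1.6 together. As written, the SAP closes the treatment-emergent period at the study completion date, so later events, and possibly those in the existing 30-day SAE period, could miss the tables. The period should end where collection ends. State also that the call does not start a further 30-day SAE period.

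Separately, reconcile Protocol 7.1.1, 7.2 and Appendix 6 on whether the children concerned leave the drug or the study. Which rule should apply is not for this review to say.

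Cost: amendment wording and one call per child not entering Study 301, with no clinic visit or blood draw. The last such completer is followed to about Day 234 instead of Day 210, 24 days longer. If the call is entered in the Schedule of Activities, the end-of-study date under 4.4 could move from Day 180 to about Day 234 for that child, 54 days.

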#### 8.3.2. Method of Detecting AEs and SAEs

The method of recording, evaluating, and assessing causality of AE and SAE and the procedures for completing and transmitting SAE reports are provided in Section [10.3](#).

Care will be taken not to introduce bias when detecting AEs and/or SAEs. Open-ended and nonleading verbal questioning of the participant or participant's parent or legal guardian is the preferred method to inquire about AE occurrences.

Study-site staff should instruct the participant's parent or legal guardian on how to report signs and symptoms (e.g., crying and pain) in the individual pediatric participant. They will be instructed to report both specific and non-specific symptoms (including vomiting, diarrhea, sleepiness, variation in the intensity and pattern of crying, etc.). These non-specific symptoms may be the only manifestations of some adverse reaction observed in neonates, infants, and toddlers.

### **8.3.3. Follow-up of AEs and SAEs**

After the initial AE/SAE report, the Investigator is required to proactively follow each participant at subsequent visits/contacts. All SAEs, and non-serious AESIs (as defined in Section 10.4.3), will be followed until resolution, stabilization, the event is otherwise explained, or the participant is lost to follow-up (as defined in Section 7.3). Further information on follow-up procedures is provided in Section 10.3.

### **8.3.4. Regulatory Reporting Requirements for SAEs**

Prompt notification (within 24 hours of learning of the event) by the Investigator to the SAE Submission Coordinator of a SAE is essential so that legal obligations and ethical responsibilities towards the safety of participants and the safety of a study intervention under clinical investigation are met.

The Sponsor has a legal responsibility to notify both the local regulatory authority and other regulatory agencies about the safety of a study intervention under clinical investigation. The Sponsor will comply with country-specific regulatory requirements relating to safety reporting to the regulatory authority, IRB/IEC, and Investigators.

For all studies, Investigator safety reports must be prepared for SUSAR according to local regulatory requirements and Sponsor policy and forwarded to Investigators as necessary.

An Investigator who receives an Investigator safety report describing a SAE or other specific safety information (e.g., summary or listing of SAEs) from the Sponsor will review and then file it along with the Investigator's Brochure and will notify the IRB/IEC, if appropriate according to local requirements.

### **8.3.5. Pregnancy**

Details will be collected of all pregnancies in female participants occurring after the start of study intervention and until 12 weeks after the last dose of study intervention.

If a pregnancy is reported, the Investigator should inform the Sponsor within 24 hours of learning of the pregnancy and should follow the procedures outlined in Section 10.5.

Abnormal pregnancy outcomes (e.g., spontaneous abortion, fetal death, stillbirth, congenital anomalies, and ectopic pregnancy) are considered SAEs.

### **8.3.6. Adverse Events of Special Interest**

See Section [10.4.3](#).

## **8.4. Treatment of Overdose**

For this study, any dose of study intervention greater than the protocol specified dose will be considered an overdose.

In the event of an overdose, the Investigator should:

1. Contact the CRO Medical Monitor immediately.
2. Closely monitor the participant for any AE/SAE and laboratory abnormalities until study intervention can no longer be detected systemically (at least 28 days).
3. Obtain a plasma sample for PK analysis if requested by the Medical Monitor (determined on a case-by-case basis).
4. Document the quantity of the excess dose as well as the duration of the overdose in the eCRF.

Decisions regarding dose continuation, dose interruptions, or modifications will be made by the Investigator in consultation with the CRO and Sponsor Medical Monitor based on the clinical evaluation of the participant.

## **8.5. Pharmacokinetics**

Blood samples will be collected for measurement of plasma concentrations of nedosiran at the timepoints specified in the SoA. Instructions for the collection and handling of biological samples will be provided in the Central Laboratory Manual. The actual date and time (24-hour clock time) of each sample will be recorded.

Pharmacokinetic parameters to be determined may include AUC,  $C_{max}$ ,  $C_{min}$ ,  $t_{max}$ , and  $t_{1/2}$ , as calculable. Additional parameters may be reported if deemed appropriate. The population PK parameters may be reported separately from the CSR.

## **8.6. Pharmacodynamics**

Pharmacodynamic parameters other than urinary oxalate and Pox (Section [8.1.1](#) and Section [8.1.2](#)) are not evaluated in this study.

## **8.7. Genetics**

Genetics will not be evaluated in this study. However, participants without documented PH genotyping must provide a DNA sample for testing at Screening.

## **8.8. Biomarkers**

See Section [8.1.1](#) and Section [8.1.2](#) for descriptions of urinary and plasma oxalate assessments.

## 8.9. Immunogenicity Assessments

Antibodies to nedosiran will be evaluated in plasma samples collected from all participants according to the SoA. Additionally, plasma samples should also be collected at the final visit from participants who discontinued study intervention or were withdrawn from the study. These samples will be tested by the Sponsor or Sponsor's designee.

The detection and characterization of antibodies to nedosiran will be performed by or under the supervision of the Sponsor.

Antibodies may be further characterized and/or evaluated for their ability to neutralize the activity of the study intervention(s). Samples may be stored for a maximum of 5 years (or according to local regulations) following the last participant's last visit for the study at a facility selected by the Sponsor to enable further analysis of immune responses to nedosiran.

## 8.10. Medical Resource Utilization and Health Economics

In order to understand how a participant's use of health care services (e.g., number of physician visits, emergency room visits) and the parent or legal guardian's out-of-pocket expenses vary across time, and if their utilization changes with PH outcomes, there will be several questions on the eCRF around medical care for PH. The parent/guardian will respond regarding the treatment for their child. Parent/guardian will be asked to report the number of physician visits (by specialty: nephrologist, urologist, PCP, and ophthalmologist) and the number of ER, urgent care, and/or inpatient visits due to the participant's PH.

Two health economics queries will also be made. The first is to ask the participant's parent/guardian what was spent out of pocket for PH treatment (i.e., hyperhydration). The second question will ask how much work time was lost to care for their child. This is only for parents/guardians employed full time outside of the home; if the parent/guardian is a full-time student, they will be asked how much classroom time was lost due to their child's PH.

### 8.10.1. Work Productivity and Activity Impairment Questionnaire: Primary Hyperoxaluria V2.0, Clinical Practice Version (WPAI:PH, V2.0, CPV) – Caregiver

The WPAI:PH, V2.0, CPV ([Reilly et al, 1993](#)) measures work productivity of the caregiver, including missed time at work, because of a child's PH. The assessment includes 6 questions related to the effect of the participant's PH on caregiver's ability to work and perform regular activities.

The 6 items are as follows:

1. currently employed
2. hours missed due to specified problem (caregiving for PH child)
3. hours missed other reasons
4. hours actually worked
5. degree problem affected productivity while working
6. degree problem affected regular activities

## 9. STATISTICAL CONSIDERATIONS

### 9.1. Statistical Hypotheses

No statistical hypothesis testing will be performed. Statistical analysis will be primarily descriptive.

### 9.2. Sample Size Determination

It is expected that approximately 25 participants will be screened, such that approximately 20 participants will complete the Day 180 assessments.

No formal sample size estimations were performed. A sample size of 20 participants was considered sufficient to provide an initial assessment of the efficacy and safety of nedosiran in pediatric participants (birth to 11 years of age) with PH1, PH2 or PH3 and relatively intact renal function.

